9.2.3 At NCI only: Blood collection for ctDNA analysis in expansion phase patients

9.2.3.1 Timing of ctDNA blood collection

Plasma, derived from whole blood collected from expansion cohort patients (as of Amendment Q, 6/14/22), will undergo ctDNA assessment by the TSO500 panel to quantitatively assess longitudinal changes in ctDNA levels (as a percentage of total circulating, cell-free DNA) and to identify any tumor genomic alterations that may be associated with response or resistance to the LMP744 treatment; the results of these studies will not be returned to patients. Once a patient has come off study, ctDNA from blood samples correlating to clinically informative time points (minimally, before treatment and at restaging scans suggesting tumor growth) will be analyzed.

Three whole blood samples of at least 7.5 mL each will be collected into three respective 10-mL Streck tubes at each of the following time points and shipped to MoCha within 3 days for ctDNA analysis:

- baseline (pre-treatment; up to 8 days prior to the start of treatment and within ± 8 hours of the biopsy at this time point)
- day 1 of every subsequent cycle (at any time)
- at time of disease progression
- 9.2.3.2 Blood specimen shipping for ctDNA analysis

Labeling:

Blood specimens should be labeled with:

- Sample type (e.g., whole blood)
- Time point (e.g., C1D1 pre-dose)
- Collection date and time
- Sample ID, containing:
 - CTEP protocol number
 - Site LAO code
 - Unique patient ID (**Do NOT include patient name, medical record number,** or initials)
 - Consecutive 800-series sample collection number (i.e., 800, 801, 802)
- The 2 tubes for each time point should be designated using "A" and "B" (e.g., the two pretreatment specimens should be labeled 800A and 800B).

For example, the sample ID for the C1D1 pre-dose ctDNA blood sample collected on Study 10002 for NCI DTC patient #004 should be: 100002_NCIDTC_004_800.

Ship blood specimens at ambient temperature to:

Attn: [name] MoCha Histology Lab Frederick National Laboratory for Cancer Research Leidos Biomedical Research, Inc. [name] [contact]

Shipment should be by CSP Courier and may be arranged by contacting [name], FNLCR, [contact].

Please contact [name] at [contact] ([contact]) to ask any questions regarding storage or shipment of these specimens. MoCha should be notified as soon as possible of all protocol deviations or issues, prior to shipment of specimens(s).

Samples should **arrive at MoCha within 2 days of collection when possible; arrival within 3 days of collection is permissible when necessary**. Note that FNLCR receiving is closed and unable to receive samples on weekends and on all Federal holidays.

10. STUDY CALENDAR

Eligibility screening evaluations (see Section 3.4) are to be performed within 8 days prior to patient enrollment, with the exception of informed consent, ECHO, and tumor imaging scans, which must be performed within 28 days prior to patient enrollment. Baseline history, physical examination, laboratory evaluations, urinalysis, and EKG are to be conducted within 8 days prior to start of protocol therapy. If protocol therapy is started within 8 days of the screening evaluations, values from the screening evaluations may be used as baseline measurements. If >8 days have passed since the screening evaluations, the medical history, physical examination, laboratory evaluations, urinalysis, and EKG must be repeated prior to starting protocol therapy. Baseline imaging scans and ECHO must be done within 28 days prior to the start of protocol therapy.

After cycle 2, the start of a new cycle may begin up to 3 days earlier than it would otherwise be scheduled or be delayed up to 1 week to accommodate scheduling conflicts and other unexpected events. History and physical examination and laboratory evaluations can be performed up to 3 days before the start of the next cycle. In the event that the patient's condition is deteriorating, laboratory evaluations should be repeated within 48 hours prior to initiation of the next cycle of therapy.

| | Pre-Study Screening | C1 D1 | C1 D2 | C1 D3 | C1 D8 | C1 D15 | C2 D1 | C2 D15 | C3 D1 | C3 D15 | Time of progression |
|--------------------------------|------------------------|---|----------|----------|----------|-----------|----------|-----------|----------|-----------|---------------------|
| LMP744 * | Screening | X | D2 | D3 | 100 | D15 | X | D15 | X | D15 | progression |
| Informed consent | X | | | | | | | | | | |
| Demographics | X | | | | | | | | | | |
| Medical history | X | | | | | | | | | | |
| Concurrent meds | X | Х | | | | | | | | X | |
| Physical exam ^c | X | Xi | | | Х | | Х | | Х | | Х |
| Vital signs | X | Xi | | | Х | | Х | | Х | | Х |
| Height | X | | | | | | | | | | |
| Weight | X | Xi | | | Х | | Х | | Х | | Х |
| Performance status | Х | X ⁱ | | | | | Х | | Х | | Х |
| CBC w/diff, plts ^a | X | Xi | | | Х | Х | Х | Х | Х | Х | Х |
| Serum chemistry ^a | X | Xi | | | Х | Х | Х | Х | Х | Х | Х |
| Urinalysis ^a | X | Xi | | | Х | Х | Х | Х | Х | Х | Х |
| Adverse event evaluation | | X | | | | | | | | X | Х |
| Tumor measurements | X | Tumor measurements are repeated per Section 11.1. Documentation (radiologic) must be provided for patients removed from study for progressive disease. | | | | | Х | | | | |
| B-HCG ^b | X | | | | | | Х | | Χ | | |
| PK sampling-blood ^d | | Х | | | Х | | | | | | |
| Blood for CTCs ^e | | Х | | Х | | | Х | | Х | | Х |
| Blood for ctDNA ^f | | Х | | | | | Х | | Х | Ī | Х |
| Tumor biopsies ^g | | Х | Х | | | | | | | | |
| ECHO/EKG ^h | X | Xi | | | | | | | Х | | |

*: LMP744 will be administered via central line. Doses as assigned; days 1-5 intravenously over 1 hour; dose escalation as defined in Section 5. After cycle 1, the infusion may be administered over 1 hour +/- 10 minutes. After cycle 2, a new cycle may begin up to 3 days earlier than it would otherwise be scheduled or be delayed up to 1 week. Monitor patients in clinic for allergic/hypersensitivity reactions for a minimum of 1 hour after receiving drug during cycle 1 and as clinically indicated thereafter.

- a: Labs (albumin, alkaline phosphatase, total bilirubin, bicarbonate, BUN, calcium, chloride, creatinine, glucose, phosphorus, potassium, total protein, SGOT (23), SGPT (10), TSH, sodium, GGT) and urinalysis will be performed at baseline/D1 of cycle 1, D8 and D15 of cycle 1, D1 and D15 of cycles 2 and 3, and then only at the start of each cycle (up to 3 days before start of a new cycle). For patients with lymphoma only, uric acid and LDH will be performed on a similar schedule. Patients on the expansion cohort will also have coagulation profile performed per Section 3.4.
- b: Urine or serum pregnancy test (women of childbearing potential) prior to every cycle.
- c: History and physical, including vital signs and weight, during weeks 1 and 2 of cycle 1, and at the start of each cycle thereafter (within 3 days prior to treatment).
- d: Blood samples for PK analyses will be collected per Section 9.1.
- e: Blood for circulating tumor cells (optional) will be collected at baseline, on cycle 1 day 3, at the start of every subsequent cycle, and at disease progression per Section 9.2.2.

- f: Blood samples for analysis of circulating tumor DNA (ctDNA) will be collected at baseline (pre-treatment, up to 8 days prior to the start of treatment and within ±8 hours of the biopsy at this time point), on cycle 1 day 2, on day 1 of every subsequent cycle (at any time), and at time of disease progression.
- g: Tumor biopsies will be collected at baseline (pre-treatment) and on cycle 1 day 2 post therapy per Section 9.2 (mandatory during the expansion phase).
- h: EKG and ECHO at baseline, up to 1 week prior to cycles 3 and 5, and as clinically indicated thereafter.
- i: Values from eligibility screening evaluations may be used as baseline (C1D1) values if test was performed within 8 days of start of protocol therapy (within 28 days of start of protocol therapy for ECHO). See Sections 3.4 and 5.

11. MEASUREMENT OF EFFECT

11.1 Antitumor Effect

11.2 Solid Tumors

Response and progression will be evaluated in this study using the international criteria proposed by the revised Response Evaluation Criteria in Solid Tumors (RECIST) guideline (version 1.1) [*Eur J Ca* 45:228-247, 2009]. Changes in the largest diameter (unidimensional measurement) of the tumor lesions and the shortest diameter in the case of malignant lymph nodes are used in the RECIST criteria.

Patients should be re-evaluated for response every 2 cycles (every 3 cycles for patients on study for more than 1 year; every 4 cycles for patients on study more than 3 years). In addition to a baseline scan, confirmatory scans should also be obtained 4 weeks following initial documentation of objective response.

11.2.1 Definitions

Evaluable for toxicity: All patients will be evaluable for toxicity from the time of their first treatment with LMP744.

Evaluable for objective response: Only those patients who have measurable disease present at baseline, have received at least one cycle of therapy, and have had their disease re-evaluated will be considered evaluable for response. These patients will have their response classified according to the definitions stated below. (Note: Patients who exhibit objective disease progression prior to the end of cycle 1 will also be considered evaluable.)

Evaluable Non-Target Disease Response: Patients who have lesions present at baseline that are evaluable but do not meet the definitions of measurable disease, have received at least one cycle of therapy, and have had their disease re-evaluated will be considered evaluable for non-target disease. The response assessment is based on the presence, absence, or unequivocal progression of the lesions.

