5.4 Duration of Therapy

In the absence of treatment delays due to adverse events, treatment may continue until one of the following criteria applies:

- Disease progression
- Intercurrent illness that prevents further administration of treatment
- DLT recurs after two dose reductions for DLT or no lower dose level exists (as described in Sections 5.1 and 6.2)
- Patient decides to withdraw from the study
- Noncompliance at the discretion of the PI

5.5 **Duration of Follow Up**

Patients will be followed for 30 days after the last dose of study drug is administered or until one of the following occurs: patient enrolls on another protocol, patient receives standard of care, or death, whichever comes first. The follow-up will consist of a phone call between Days 27-30 after the last dose to evaluate adverse events that were ongoing and any new events that might be deemed related to the therapy. Unacceptable toxicities (i.e., AEs related to the intervention) that have not resolved by Day 30 post-treatment will be followed via biweekly phone calls until stabilization or resolution.

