6.3 Dose and Cycle delays

Subsequent cycles may be delayed up to 14 days past the end of the previous cycle of 28 days for resolution of toxicity. Patients will be allowed up to 2 dose reductions. If more than 2 dose reductions are required, the patient will be removed from the study. For patients on dose level 1, only 1 dose reduction will be allowed (see Section 5.1.2).

6.4 **Reporting and Exclusions**

6.4.1 Evaluation of toxicity: A cycle is defined as being 28 days, with Day 1 starting the first day of the 5-day treatment. All patients who receive a dose of LMP744 will be evaluable for toxicity regardless of whether they complete a cycle. If therapy is delayed, the next cycle day 1 will be the day therapy is administered.

Patients who do not complete a cycle of therapy for reasons other than toxicity will be replaced.

6.4.2 Evaluation of response: All patients included in the study who receive any treatment at all will be assessed for response to treatment, even if there are major protocol treatment deviations or if they are ineligible. All patients who meet the eligibility criteria will be included in the main analysis of the response rate. Secondary analyses may be restricted to patients without major protocol violations.

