11.2.4.3 Evaluation of Best Overall Response

The best overall response is the best response recorded from the start of the treatment until disease progression/recurrence (taking as reference for progressive disease the smallest measurements recorded since the treatment started). The patient's best response assignment will depend on the achievement of both measurement and confirmation criteria.

| Target Lesions | Non-Target Lesions | New Lesions | Overall Response | Best Overall Response when Confirmation is Required* | | |
|-------------------|-----------------------|-------------|---------------------|---|--|--|
| CR | CR | No | CR | >4 wks. Confirmation** | | |
| CR | Non-CR/Non-PD | No | PR | | | |
| CR | Not evaluated | No | PR | >1 when Confirmation** | | |
| PR | Non-CR/Non- | No | PR | \geq 4 wks. Confirmation** | | |
| | PD/not evaluated | | | | | |
| SD | Non-CR/Non- | No | SD | Documented at least once ≥ 4 wks. | | |
| | PD/not evaluated | | | from baseline** | | |
| PD | Any | Yes or No | PD | | | |
| Any | PD*** | Yes or No | PD | no prior SD, PR or CR | | |
| Any | Any | Yes | PD | | | |
| * See RECIS | | | | | | |

For Patients with Measurable Disease (*i.e.*, Target Disease)

** Only for non-randomized trials with response as primary endpoint.

*** In exceptional circumstances, unequivocal progression in non-target lesions may be accepted as disease progression.

Note: Patients with a global deterioration of health status requiring discontinuation of treatment without objective evidence of disease progression at that time should be reported as "symptomatic deterioration." Every effort should be made to document the objective progression even after discontinuation of treatment.

For Patients with Non-Measurable Disease (i.e., Non-Target Disease)

| Non-Target Lesions | New Lesions | Overall Response |
|--------------------|-------------|------------------|
| CR | No | CR |
| Non-CR/non-PD | No | Non-CR/non-PD* |
| Not all evaluated | No | not evaluated |
| Unequivocal PD | Yes or No | PD |
| Any | Yes | PD |

'Non-CR/non-PD' is preferred over 'stable disease' for non-target disease since SD is increasingly used as an endpoint for assessment of efficacy in some trials so to assign this category when no lesions can be measured is not advised

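### Do Sections 6.4.2 and 11.2.1 leave the response-rate denominator open for patients who are never rescanned or are replaced?

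*Combined protocol and SAP*

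**What the plan says.** Section 6.4.2 has everyone who receives any treatment assessed for response, including ineligible patients and those with major deviations. It then fixes the main analysis: "All patients who meet the eligibility criteria will be included in the main analysis of the response rate". The only secondary analysis it mentions may leave out major protocol violations.

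Section 11.2.1, under Solid Tumors in the chapter on measurement of effect, restricts the group whose tumor response can be judged as follows: "Only those patients who have measurable disease present at baseline, have received at least one cycle of therapy, and have had their disease re-evaluated". Its next sentence says that these patients have their response classified by the definitions that follow. A note adds: "Patients who exhibit objective disease progression prior to the end of cycle 1 will also be considered evaluable". A parallel class covers patients with only non-measurable lesions. They too need one cycle, and those who "have had their disease re-evaluated will be considered evaluable for non-target disease".

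Other passages that bear on the point:

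- Section 6.4.1: "Patients who do not complete a cycle of therapy for reasons other than toxicity will be replaced".
- Section 11.2: "Patients should be re-evaluated for response every 2 cycles" (less often after the first year).
- Section 5.5: "The follow-up will consist of a phone call between Days 27-30 after the last dose to evaluate adverse events that were ongoing". The call also covers new events thought to be related. Unresolved related toxicity is then followed by biweekly calls.
- Section 11.2.4.3: the table for non-measurable disease has a row "Not all evaluated". The table for measurable disease has no row for target lesions that were never reassessed. A note gives a reporting label for patients who stop because of general deterioration without objective progression, and asks sites to try to document progression afterwards.
- Sections 1.3 and 13.3: antitumor activity is exploratory, and exploratory results are to carry caveats. Section 13 names no response denominator, target or test.

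**The concern.** The two sets differ. Section 3.1.2 admits patients with measurable or merely evaluable disease, and Section 6.4.2 requires neither a completed cycle nor a rescan. Section 11.2.1 requires measurable disease, a cycle and a rescan, and opens with a restrictive phrase that can be read as defining an analysis set.

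The affected patient is easy to foresee. Someone who leaves after cycle 1 without documented progression reaches the follow-up call before the first scheduled restaging and may never have a post-baseline scan. A patient who stops during cycle 1 for a reason other than toxicity is replaced, and Section 6.4.1 does not mention response status.

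If an analyst used the Section 11.2.1 set, unscanned patients would leave the denominator but could not leave the numerator, so any non-zero rate would rise. A denominator chosen after the results are known would be a weakness even for an exploratory endpoint.

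**Working it through.** The plan states no response rate, target or response-based sample size, so it has no figure to reproduce. The check is a comparison of the text, followed by an illustration of scale.

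**1. Is the patient without a scan foreseeable?** The last cycle 1 dose is on day 5. The call falls on days 5 + 27 = 32 to 5 + 30 = 35. Two 28-day cycles end on day 2 × 28 = 56. The gap is 56 − 35 = 21 to 56 − 32 = 24 days. The case is real.

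**2. Which passage sets the denominator?** Section 6.4.2 names the main analysis of the response rate and who is in it. Section 11.2.1 mentions no rate, denominator or analysis set; the stated consequence of being evaluable is that a response category is assigned. One section says who is counted, the other whose response is graded.

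**3. Where does each awkward patient fall under Section 6.4.2?**

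| Eligible, treated patient | In the 6.4.2 denominator? | Can be in the numerator? |
|---|---|---|
| Completed a cycle, never rescanned | Yes | No, no response documented |
| Replaced under 6.4.1, never rescanned | Yes, no exception is made | No, no response documented |
| Objective progression before the end of cycle 1 | Yes | No, progression |

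Replacement fills a place. It does not take the replaced patient out of Section 6.4.2.

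**4. Would an explicit non-responder rule change the main rate?** Let n be the eligible patients, u those without a post-baseline assessment and r the responders. As written, the rate is r/n. Under an explicit rule it is (r + 0 × u)/n = r/n. They are the same.

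**5. What if the narrower set were used anyway?** Dropping only unassessed patients gives r/(n − u), larger by n/(n − u) = 1/(1 − d), where d = u/n. The plan gives no d. For assumed d of 10%, 20% and 30% the factor is 1.11, 1.25 and 1.43.

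- *Whole trial.* Section 13.2 has a maximum of 47 patients and a ceiling of 53, so 53 − 47 = 6 places are reserved for patients who may not be evaluable. If all 6 were eligible but unassessed, d = 6/53 = 11.3%. With 3 assumed responders: 3/53 = 5.7% (exact 95% CI 1.2 to 15.7) against 3/47 = 6.4% (1.3 to 17.5).
- *Expansion cohort.* Assume 15 eligible solid-tumor patients with measurable disease and 2 responders. With 3 unscanned: 2/15 = 13.3% (1.7 to 40.5) against 2/12 = 16.7% (2.1 to 48.4).
- *Replacement.* Assume 15 assessed, 2 responders and 1, 2 or 3 further eligible patients replaced and unscanned. Section 6.4.2 gives 2/16 = 12.5%, 2/17 = 11.8% or 2/18 = 11.1%, against 2/15 = 13.3% in the narrower set.

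The upward direction holds for unscanned patients only. The measurable-disease condition could also remove a responder, such as a complete response in non-measurable disease, so the net effect of the full switch has no fixed sign.

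**The case for a change.** The best case for a change is that the division of labor between the two sections has to be inferred. Neither cites the other, Section 13 is silent, and the wording of Section 11.2.1 invites use as an analysis set. An eligible patient with measurable disease who is never rescanned has no category in the best-response table. The deterioration note covers only some early leavers and does not say whether they are counted. The general caveat in Section 13.3 would not tell a reader which denominator was used. A few sentences would settle it and need no new data.

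Most of this is accurate as description: the cross-reference is absent, the label is absent, and a rate in the Section 11.2.1 set has no stated role. It does not show that the main denominator is open. The inflation in step 5 needs an analyst to pass over the one sentence that names the main analysis. The missing category affects how such a patient is listed in a table of best response. It cannot move the main rate, because a patient with no documented response adds nothing to the numerator under any label.

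**Conclusion.** The concern does not call for a change. The plan already names the main response-rate set, and followed as written it gives the same rate as an explicit non-responder rule. The gap is one of linkage and labeling. An analyst would ordinarily fill it by using the Section 6.4.2 denominator, listing patients without a post-baseline assessment as not evaluated, and reporting their number.

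Departing from the text could multiply a non-zero rate by 1.11 to 1.43 for assumed unassessed fractions of 10% to 30%. The Section 13.2 allowance, which does not say what patients may not be evaluable for, is only a rough anchor; it corresponds to about 11%, or 53/47 = 1.13. In each example where both intervals are shown, the shift is small beside their width.

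This conclusion assumes that Section 6.4.2 is read literally for eligible treated patients and that response stays exploratory. No dose decision, DLT count, MTD or sample size depends on the response rate.

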11.2.2 Disease Parameters

Measurable disease: Measurable lesions are defined as those that can be accurately

measured in at least one dimension (longest diameter to be recorded) as $\geq 20 \text{ mm} (\geq 2 \text{ cm})$ by chest x-ray or as $\geq 10 \text{ mm} (\geq 1 \text{ cm})$ with CT scan, MRI, or calipers by clinical exam. All tumor measurements must be recorded in millimeters (or decimal fractions of centimeters).

Note: Tumor lesions that are situated in a previously irradiated area might or might not be considered measurable.

Malignant lymph nodes: To be considered pathologically enlarged and measurable, a lymph node must be $\geq 15 \text{ mm} (\geq 1.5 \text{ cm})$ in short axis when assessed by CT scan (CT scan slice thickness recommended to be no greater than 5 mm [0.5 cm]). At baseline and in follow-up, only the short axis will be measured and followed.

Non-measurable disease: All other lesions (or sites of disease), including small lesions (longest diameter <10 mm [<1 cm] or pathological lymph nodes with \geq 10 to <15 mm [\geq 1 to <1.5 cm] short axis), are considered non-measurable disease. Bone lesions, leptomeningeal disease, ascites, pleural/pericardial effusions, lymphangitis cutis/pulmonitis, inflammatory breast disease, and abdominal masses (not followed by CT or MRI), are considered as non-measurable.

Note: Cystic lesions that meet the criteria for radiographically defined simple cysts should not be considered as malignant lesions (neither measurable nor non-measurable) since they are, by definition, simple cysts. 'Cystic lesions' thought to represent cystic metastases can be considered as measurable lesions, if they meet the definition of measurability described above. However, if non-cystic lesions are present in the same patient, these are preferred for selection as target lesions.

Target lesions: All measurable lesions up to a maximum of 2 lesions per organ and 5 lesions in total, representative of all involved organs, should be identified as **target lesions** and recorded and measured at baseline. Target lesions should be selected on the basis of their size (lesions with the longest diameter), be representative of all involved organs, but in addition should be those that lend themselves to reproducible repeated measurements. It may be the case that, on occasion, the largest lesion does not lend itself to reproducible measurement in which circumstance the next largest lesion which can be measured reproducibly should be selected. A sum of the diameters (longest for non-nodal lesions, short axis for nodal lesions) for all target lesions will be calculated and reported as the baseline sum diameters. If lymph nodes are to be included in the sum, then only the short axis is added into the sum. The baseline sum diameters will be used as reference to further characterize any objective tumor regression in the measurable dimension of the disease.

Non-target lesions: All other lesions (or sites of disease) including any measurable lesions over and above the 5 target lesions should be identified as **non-target lesions** and should also be recorded at baseline. Measurements of these lesions are not required, but the presence, absence, or in rare cases unequivocal progression of each should be noted throughout follow-up.

